A mixed model for repeated measures (MMRM) will be used to analyze the difference in postoperative MADRS score which is our primary outcome. The model will include treatment and time as fixed effects, with a treatment*time interaction term. The data will be modeled with random intercepts and random slopes to account for variation in baseline scores and postoperative trajectories. MADRS scores measured on postoperative Day 1, 2, and 3 will be combined and treated as a single timepoint in the mixed model, rather than separately testing each day for significance which can inflate type I error rate. Postoperative Days 1, 2, and 3 were chosen due to previously published data showing that the antidepressant effect of ketamine persists up to 3 days after administration.

27b. Sensitivity analyses

Sensitivity analyses will be conducted for the following scenarios:

- 1) Missing data: See section 28
- 2) Intention-to-treat vs per-protocol analysis (if needed)
- 3) MMRM analysis using HADS (self-report) as a confirmatory measure
- 4) MMRM analysis using the previously proposed primary outcome measure (a composite score defined as the sum of scores from MADRS and HADS)

27c. Subgroup analyses

We will conduct several pre-specified subgroup analyses. While the trial will not specifically be powered for these subgroups, we hope to gain further insight into sub-populations that may particularly benefit from the intervention. Example subgroup analyses to be considered:

- 1) Preoperative use of antidepressants
- 2) Preoperative use of opioids
- 3) Intraoperative exposure to nitrous oxide
- 4) Intraoperative exposure to opioid infusions
- 5) Postoperative use of neuraxial or peripheral nerve catheters

28. Missing data

For the primary outcome, it will be assumed that the missing data are missing at random. Sensitivity analysis will be performed to evaluate the robustness of the MMRM to the missing-at-random assumption.

29. Adverse events

Adverse events will be recorded in the Stanford REDCap database using the Adverse Event (AE) Form and Serious Adverse Event (SAE) Form. Refer to document GUI-P13 (<https://researchcompliance.stanford.edu/panels/hs/policies/guidances>) for definitions of AEs and SAEs. All AEs and SAEs will be summarized.

30. Statistical software

Statistical analyses will be conducted using R statistical software. Data figures for visualization will be generated using either R or Graphpad Prism.

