The first 5 patients that meet inclusion/exclusion criteria will be entered into the open-label feasibility study; all will receive a ketamine infusion. All other patients enrolled thereafter will be entered into the double-blind, randomized, placebo-controlled study. The day of surgery will be considered Day 0 of the study. Baseline assessments must be performed before the patient receives any psychoactive premedication (e.g. midazolam, fentanyl, gabapentin, oxycodone). Assessments will be performed either in the hospital or, if the patient has been discharged (typically on postoperative Day 2), by phone.

Participants who remain in the hospital for at least 24 hours post-surgery will be asked to give blood samples for immunological analyses. Two blood samples (10mL for each draw) will be collected from each participant.

Day 0 (Baseline Assessments):

By Physician or Study Staff:

- Vital Signs
- Concomitant Medication Review
- Adverse Events Review
- Montgomery-Asberg Depression Rating Scale (MADRS)
- Collect breath sample #1

By the Participant, reviewed by Investigators:

- Hospital Anxiety and Depression Scale (HADS)
- Brief Pain Inventory (BPI)

Day 0 (During Surgery):

By the Intraoperative Anesthesiologist:

- Ketamine infusion or placebo (saline) infusion
- Continuous physiological monitoring
- SedLine® Brain Function Monitor to evaluate depth of anesthesia/sedation
- Collect breath sample #2, after infusion is complete

Day 1:

By Physician or Study Staff:

- Vital Signs
- Concomitant Medication Review
- Adverse Events Review
- Montgomery-Asberg Depression Rating Scale (MADRS)

By the Participant, reviewed by Investigators:

- Hospital Anxiety and Depression Scale (HADS)
- Brief Pain Inventory (BPI)

Day 2:

By Physician or Study Staff:

- Vital Signs (inpatient only)
- Concomitant Medication Review
- Adverse Events Review
- Montgomery-Asberg Depression Rating Scale (MADRS)

By the Participant, reviewed by Investigators:

- Hospital Anxiety and Depression Scale (HADS)
- Brief Pain Inventory (BPI)

Day 3 (inpatient or via phone):

By Physician or Study Staff:

- Vital Signs (inpatient only)
- Concomitant Medication Review
- Adverse Events Review
- Montgomery-Asberg Depression Rating Scale (MADRS)

By the Participant, reviewed by Investigators:

- Hospital Anxiety and Depression Scale (HADS)
- Brief Pain Inventory (BPI)

Day 5 (inpatient or via phone):

By Physician or Study Staff:

- Vital Signs (inpatient only)
- Concomitant Medication Review

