This is a single-site phase IV randomized clinical trial utilizing a quadruple-masked, placebo-controlled, parallel arm design. Participants will be randomly allocated in a 1:1 ratio to one of two groups: Group A (n=20) will receive a ketamine infusion of 0.5 mg/kg over 40 min during surgery. Group B (n=20) will receive a saline infusion over 40 min during surgery. In both groups, the study drug will be given after anesthetic induction. The participants, care providers, investigators, and outcomes assessors will be masked.

10. Randomization

Participants will be sequentially randomized as they enter the study. We will employ block randomization with 5 blocks of 8 patients each.

11. Sample size

We will enroll a total of 40 participants. Our sample size calculation was derived from an *a priori* power analysis for the primary outcome measure with a 1:1 allocation ratio. In a randomized controlled trial of ketamine vs active placebo (midazolam) performed by

Phillips et al. (2019), participants had a mean decrease of 10.9 points (SD=8.9) in MADRS total score relative to pre-infusion scores compared with a mean decrease of 2.8 points (SD=3.6) with midazolam. Using these results, we computed an estimated total sample size of 38 participants at a two-sided alpha level of 0.05 and 80% power. An additional 2 participants were added to account for potential attrition, for a total of 40 participants. Given the increased statistical efficiency of mixed models for repeated measures (MMRM) compared to parametric pre-post tests, we assumed that 40 participants should be sufficient to power our study for MMRM analysis.

12. Framework

We plan to evaluate the antidepressant superiority of ketamine to placebo by assessing the postoperative MADRS scores from postoperative Day 1 through Day 3. Additional outcomes collected at postoperative Day 5, 7, and 14 will be used for statistical model building and exploratory analyses.

13. Interim data monitoring

13a. Statistical interim analyses planned and time points

No statistical interim analyses planned.

13b. Any planned adjustment of significance level due to interim analysis

N/A.

13c. Details of guidance for stopping the trial early

N/A.

14. Timing of final analysis

Once all data have been collected at all planned time points from the final (40th) participant, all investigators will be unmasked and all outcomes will be analyzed together in the final analysis.

15. Timing of outcome assessments

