4. Diagnosed with Major Depressive Disorder (MDD), single or recurrent, and currently experiencing a Major Depressive Episode (MDE) of at least 4 weeks in duration, prior to screening, according to the criteria defined in the Diagnosis and Statistical Manual of Mental Disorders, Fifth Edition. The diagnosis of MDD will be made by a trained study staff member and supported by the Mini International Neuropsychiatric Interview - Module A.
5. Meet the threshold on the total combined HADS-MADRS score of ≥ 31 at both screening and day of surgery visits.
6. In sufficiently good health to proceed with planned surgery, as ascertained by a standard preoperative clinic evaluation which includes medical history, physical examination (PE), clinical laboratory evaluations, any indicated cardiac testing, and final clearance by the attending anesthesiologists on the day of surgery.
7. Body mass index between 17-40kg/m².

8. Concurrent psychotherapy will be allowed if the type (e.g., supportive, cognitive behavioral, insight-oriented, et al) and frequency (e.g., weekly or monthly) of the therapy has been stable for at least 4 weeks prior to screening and if the type and frequency of the therapy is expected to remain stable during the course of the subject's participation in the study.

9. Concurrent antidepressant therapy (e.g. SSRI or SNRI) and/or hypnotic therapy (e.g. zolpidem, zaleplon, melatonin, or trazodone) will be allowed if the therapy has been stable for at least 4 weeks prior to screening and if it is expected to remain stable during the course of the subject's participation in the study.

22b. Exclusion criteria

A potential participant will NOT be eligible for participation in this study if any of the following criteria are met:

1. Female that is pregnant or breastfeeding. These women would not be candidates for elective surgery under any circumstances, and therefore would be screened out from our study population at their routine preoperative evaluation. Women of childbearing potential are routinely screened for pregnancy at their preoperative visit by urine hCG testing if clinically indicated. We will not be including pregnant women from other surgical populations as well.

2. Total HADS-MADRS score of <31 at either the screening or day of surgery visits.

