12. History of hyperthyroidism which was treated (medically or surgically) less than six months prior to screening.
13. Any current or past history of any physical condition which in the investigator's opinion might put the subject at risk or interfere with study results interpretation.
14. Patients currently maintained on high dose opioids (>90 morphine equivalents per day) prior to surgery

23. Recruitment

Information to be collected and reported in CONSORT flow diagram include:

Patients with a history of depression screened
Excluded due to PHQ score < 12
Excluded due to other exclusion criteria
Declined to participate
Lost to follow-up during screening
Excluded after consent
Withdrew after consent prior to intervention
Participants consented

24. Withdrawal and follow-up

24a. The following withdrawal/lost to follow-up data will be recorded:

- Number of participants who withdraw or are lost to follow-up
- Timing of withdrawal or lost to follow-up
- Reasons of withdrawal or lost to follow-up

24b. The above withdrawal/lost to follow-up data will be presented as:

- Percentages (%) of participants who withdraw or are lost to follow-up
- Kaplan-Meier curves of withdrawal or lost to follow-up (if any)
- Reasons of withdrawal or lost to follow-up summarized in the Results section

25. Baseline patient characteristics

25a. List of baseline characteristics to be reported

- 1) Sex (n, %)
- 2) Age (years, mean and SD)
- 3) Body mass index (mean, SD)
- 4) Hispanic/Latino ethnicity (n, %)
- 5) Race
 - a. White (n, %)
 - b. Black/African American (n, %)
 - c. Asian (n, %)
 - d. Native Hawaiian/Pacific Islander (n, %)
 - e. Other (n, %)
 - f. Unknown (n, %)
- 6) Married (n, %)
- 7) Disabled (n, %)
- 8) Current smoker (n, %)
- 9) PHQ score at screening (points, mean and SD)
- 10) HADS at screening (points, mean and SD)
- 11) MADRS at screening (points, mean and SD)
- 12) HADS-MADRS composite score at screening (points, mean and SD)
- 13) Age at first MDD onset (years, mean and SD)
- 14) Duration of current episode (months, mean and SD)
- 15) Recurrent major depression (n, %)
- 16) Previous clinical ketamine exposure (n, %)
- 17) Previous recreational ketamine exposure (n, %)
- 18) Charlson Comorbidity Index (points, mean and SD)
- 19) Maudsley resistance stage (points, mean and SD)
- 20) Numerical pain score (points, mean and SD)
- 21) Pain interference from BPI (points, mean and SD)

25b. Preoperative psychoactive medications

- 1) Opioids (n, %)

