- 2) MME/day, if on opioids (mean, SD)
- 3) Anticonvulsants (n, %)
- 4) Benzodiazepines (n, %)
- 5) Muscle relaxants (n, %)
- 6) Antidepressants (n, %)
- 7) Antipsychotics (n, %)
- 8) Lithium (n, %)
- 9) Prescription sleep medications (n, %)
- 10) Opioid antagonists (n, %)
- 11) Stimulants (n, %)

25c. Surgical characteristics

- 1) Type of surgery
 - a. ENT/OMF (n, %)
 - b. Thoracic (n, %)
 - c. Breast (n, %)
 - d. Plastic non-breast (n, %)
 - e. Spine (n, %)
 - f. Major joint (n, %)
 - g. Other orthopedic/limb (n, %)
 - h. Intraabdominal general surgery (n, %)
 - i. Urologic and gynecologic (n, %)
 - j. Vascular (n, %)
 - k. Transplant (n, %)
- 2) Type of anesthesia
 - a. General anesthesia (n, %)
 - b. Monitored anesthesia care (n, %)
- 3) Intraoperative nitrous oxide (n, %)
- 4) Intraoperative propofol infusion (n, %)
- 5) Intraoperative opioid infusion (n, %)
- 6) Length of surgery (hours, mean and SD)
- 7) Peripheral or neuraxial catheter placed (n, %)

Section 6: Analysis

26. Outcome definitions

26a. Primary outcome

Postoperative MADRS scores from postoperative Days 1 through 3.

26b. Main secondary outcomes

- 1) Proportion of participants with clinical response (defined as a $\geq 50\%$ reduction in MADRS score from baseline).
- 2) Proportion of participants with remission (defined as a MADRS score of ≤ 12 on day 14).

26c. Other exploratory secondary outcomes

- 1) MADRS scores at postoperative Days 5, 7, and 14
- 2) Hospital Anxiety and Depression Scale
- 3) Cumulative inpatient opioid use
- 4) Hospital length of stay
- 5) Average inpatient opioid use per day
- 6) Opioid use at postop day 7
- 7) Opioid use at postop day 14
- 8) Postoperative numeric pain scores
- 9) Postoperative pain interference scores

27. Analysis methods

27a. Analysis of the primary outcome

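### SAP 27a gives the primary model no baseline MADRS adjustment and does not say how Day 0 enters; adjusting for Day 0 is an almost free gain in precision

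*SAP*

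**What the plan says.** SAP 26a defines the primary outcome as "Postoperative MADRS scores from postoperative Days 1 through 3". For its analysis, SAP 27a states: "The model will include treatment and time as fixed effects, with a treatment*time interaction term". Days 1, 2 and 3 are merged into one timepoint. Baseline appears in 27a only in the random-effects sentence, which calls for "random intercepts and random slopes to account for variation in baseline scores and postoperative trajectories". No baseline covariate is named there, in the sensitivity analyses of 27b, or in item 3 of the Protocol's analysis plan (section 8C).

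SAP 11 sizes the trial on change from pre-infusion scores and then relies on the model being more efficient: "Given the increased statistical efficiency of mixed models for repeated measures (MMRM) compared to parametric pre-post tests". SAP 12 adds: "Additional outcomes collected at postoperative Day 5, 7, and 14 will be used for statistical model building and exploratory analyses".

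A Day 0 MADRS exists. Protocol 8D lists it under the Day 0 baseline assessments and requires: "Baseline assessments must be performed before the patient receives any psychoactive premedication". SAP 15 also describes a repeat baseline on the morning of surgery, although it calls this a questionnaire, whereas SAP 4b describes the MADRS as clinician-administered. The exclusion rule in SAP 22b, "Total HADS-MADRS score of <31 at either the screening or day of surgery visits", cannot be applied without a Day 0 score. The baseline table in SAP 25a lists MADRS at screening only.

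**The concern.** The wording about variation in baseline scores suggests that baseline is taken care of. A random intercept models the correlation among a patient's scores; with complete data it does not condition the arm comparison on the Day 0 score. Two analyses fit the text:

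- **Difference in change.** Day 0 is a response row and treatment*time is the test. SAP 11 points this way, and so does the mention of baseline scores in 27a.
- **Post-only.** Only postoperative rows are modelled. SAP 26a and SAP 12 leave this open.

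Neither is adjusted for Day 0, and a Day 0-adjusted contrast is generally at least as precise as either. With 20 per arm, and a sample-size section that counts on the model's efficiency, precision matters. The two readings can also differ in power, so the choice between them should be fixed before unblinding.

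**Working it through.** **Reproducing SAP 11.** The mean difference is 10.9 - 2.8 = 8.1 points. With SD 8.9 in both arms, n per arm = 2 × (1.96 + 0.842)² × 8.9² / 8.1² = 18.95, so 19 per arm and 38 in total, as stated. With the root-mean-square of the two quoted SDs, √((8.9² + 3.6²)/2) = 6.79, the same formula gives 24 in total. The stated 38 therefore matches SD 8.9 in both arms. By noncentral t, a single-day change score with SD 8.9 and 20 per arm has 80.1% power.

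**What the model in 27a estimates with complete data.** In simulated trials with one Day 0 row and three postoperative rows, the treatment*time estimate equalled the between-arm difference in (Day 1-3 mean minus Day 0) to 1e-12. With postoperative rows only, the treatment estimate equalled the plain difference in Day 1-3 means. Equal weighting of the three days is not guaranteed. With random slopes on calendar day (assumed slope SD 1 point per day, residual SD 4), the generalised least squares weights on Days 1, 2 and 3 are 0.44, 0.33 and 0.22. Day 0 still has weight -1, so the contrast remains an unadjusted change.

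**Assumed inputs (not in the documents).** Baseline-to-follow-up correlation r = 0.3, 0.5, 0.7; between-day correlation d = 0.7, 0.8; ratio of Day 0 SD to follow-up SD k = 1, 0.8, 0.5. SD 8.9 is taken as the single-day change SD.

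**Formulas.** Follow-up SD s = 8.9/√(1 + k² - 2rk); v = (1 + 2d)/3. For the Day 1-3 mean:

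- SD of change = s√(v + k² - 2rk)
- SD post-only = s√v
- SD adjusted = s√(v - r²), with variance multiplied by 37/36 for estimating the baseline slope, and 37 rather than 38 degrees of freedom

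The 95% CI half-width is t × SD × √(2/20), with the 37/36 factor inside the root for the adjusted contrast.

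**Two worked cells (r = 0.5, d = 0.8, so v = 0.867).**

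- k = 1: s = 8.9. Change SD = 8.9√0.867 = 8.29, power 85.4%, half-width 5.30. Adjusted SD = 8.9√0.617 = 6.99, power 94.1%, half-width 4.54.
- k = 0.5: s = 8.9/√0.75 = 10.28. Change SD and adjusted SD are both 10.28√0.617 = 8.07. The regression slope r/k is 1, so change is already the best contrast and adjustment only pays its cost: power 87.1% against 86.2%, half-width 5.17 against 5.24.

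**Whole grid, 8.1 points, 20 per arm.**

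| k | Change power | Adjusted power | Adjusted minus change (points) | Post-only power | Implied follow-up SD |
|---|---|---|---|---|---|
| 1 | 84-93% | 94-97% | +4 to +12 | 65-96% | 7.5-11.5 |
| 0.8 | 85-95% | 90-95% | 0 to +8 | 58-92% | 8.3-12.3 |
| 0.5 | 86-94% | 86-96% | -1 to +2 | 61-86% | 9.1-12.0 |

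Against change, the adjusted half-width runs from about 0.1 point wider to about 1.2 points narrower. The adjusted contrast is never more than about 1 power point below the better of the two unadjusted readings. Simulation (20,000 trials per cell) agreed within 0.01, and the adjusted test's type I error was 0.047-0.052.

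**If both quoted SDs apply (pooled 6.79).** Change has 97% power or more throughout. Adjustment adds at most about 3 points and narrows the half-width by up to 0.9.

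**Cost of the covariate.** At r = 0 the variance rises by 37/36 - 1 = 2.8% against post-only. Break-even is a correlation of √(1/37) = 0.16 between Day 0 and the Day 1-3 mean. The critical t moves from 2.024 to 2.026.

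**The case against.** The strongest reply is that the plan is valid as written, the choice is between acceptable methods, and the likely gain is small. Much of this stands. On the likelier reading, the gain exceeds 8 points only when Day 0 scores vary as much as follow-up scores (k = 1). The HADS-MADRS entry threshold of 31 cuts off low Day 0 scores but not low follow-up scores, which makes k below 1 plausible. The threshold may also lower r, which raises the gain at k = 1 or 0.8, so it does not settle the size.

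Three stronger readings might be inferred, and the documents support none of them:

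- **Bias or an inflated type I error.** Allocation is randomized, and both unadjusted contrasts are unbiased.
- **The mixed model is no more than a pre-post test.** The exact equality holds with equal weighting of days and complete data. The SAP does not state how slope time is coded, averaging days is itself a gain, and under the missing-at-random assumption of SAP 28 a Day 0 row is partly used when follow-up is missing.
- **Some 30 points of power are at risk.** Differences that large (the grid runs from +1 to +33 against post-only) belong to the less likely post-only reading and need implied follow-up SDs of about 11 to 12.

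Nor is the SAP silent on a morning-of-surgery baseline, since SAP 15 describes one. That does not answer the point, because 27a neither uses it nor names the primary coefficient.

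**Conclusion.** The point holds as an inexpensive improvement in precision and prespecification that should be made. SAP 27a contains no baseline-adjusted treatment contrast and leaves open both the role of Day 0 and the coefficient to be tested. Against difference in change, adjustment is worth about -1 to +12 power points with SD 8.9 in both arms, and at most about 3 points, mainly as a narrower interval, if the pooled SD of 6.8 applies. These figures rest on the assumed correlations and SD ratio, on the SAP 11 effect carrying over to the Day 1-3 mean, and on complete data. The conclusion that the contrast is unadjusted does not depend on the assumed values.

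**What to change.** Before unblinding, amend SAP 27a to:

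- name the Day 0 pre-premedication MADRS as baseline, consistent with Protocol 8D and the repeat baseline of SAP 15;
- either enter it as a fixed covariate, or keep Day 0 as a response row with a common baseline mean across arms;
- define the primary effect as the baseline-adjusted between-arm difference over Days 1-3.

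Use the same approach for the HADS and composite models in 27b. Adding Day 0 MADRS to the 25a table is optional.

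The cost is a few sentences and about one degree of freedom. Variance rises by at most about 3% against post-only if the correlation is near zero, and about 1 power point is lost against change in some scenarios. No new data are needed.

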STATISTICAL ANALYSIS PLAN

Official Title:

Intraoperative Ketamine Versus Saline in Depressed Patients
Undergoing Anesthesia for Non-cardiac Surgery

NCT Number: 03861988

Protocol last edited: 10/28/2021

Statistical Analysis Plan (SAP)

Section 1: Administrative Information

1. Title and trial registration

1a. Title

Intraoperative Ketamine Versus Saline in Depressed Patients Undergoing Anesthesia for Non-Cardiac Surgery

1b. Trial registration number

ClinicalTrials.gov Identifier NCT# 03861988

2. SAP version: 2.0

3. Protocol version: Stanford eProtocol ID 49114, last revision submitted 8/9/21

4. SAP revisions

4a. SAP revision history

10/21/2019 – version 1.0 (originally included in the study protocol)

10/28/2021 – version 2.0 (created a new, separate SAP document)

4b. Justification for each SAP revision

Version 1.0 to 2.0:

- 1) In our original protocol, recruitment was limited to patients with symptomatic depression presenting for hip and knee arthroplasty at Stanford. Patients undergoing this type of surgery have a predictable postoperative course, which guided our primary endpoint selection. We encountered significant difficulties recruiting patients during the COVID-19 pandemic. Therefore, we expanded eligibility criteria by including patients presenting for a wider variety of surgical procedures, which are described in our updated protocol. To account for the likely increased variability of postoperative recovery in this broader population, we updated our primary endpoint to include data from the first 3 days after surgery, instead of only a single day after surgery.
- 2) In our original protocol, the primary outcome measure was defined as the sum of scores from a clinician-administered scale and a self-report scale. During the recruitment phase of our trial, and prior to unblinding, we presented our analysis plan to a panel of statisticians in the Department of Biomedical Data Sciences at Stanford University. The panel recommended that we could improve the interpretability and reduce the variance in our primary outcome by only using one validated measure (rather than a composite score) as our primary outcome measure. Based on this recommendation, we updated our primary outcome measure to only include the clinician-administered scale (the Montgomery-Asberg Depression Rating Scale).

4c. Timing of SAP revisions

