All patients will have at least one baseline psychiatric assessment prior to Day 0. Repeat baseline assessment by questionnaire will occur on the morning of surgery prior to any preoperative medication being given. The study assessments will be performed at postoperative Day 1, Day 2, Day 3, Day 5, Day 7 and Day 14. Assessments will be performed either in hospital or by phone or video.

Section 4: Statistical Principles

16. Level of statistical significance

We will use an uncorrected two-sided alpha of 0.05 as a cutoff for statistical significance.

17. Adjustment for multiplicity and controlling type I error

The primary outcome (MADRS score) that is measured on postoperative Day 1, 2, and 3 will be combined and treated as a single timepoint in the mixed model, rather than separately testing each day for significance which can inflate type I error rate.

Postoperative Days 1, 2, and 3 were chosen due to previously published data showing that the antidepressant effect of ketamine persists up to 3 days after administration.

18. Confidence intervals to be reported

We will report 95% confidence intervals for the primary outcome.

19. Adherence and protocol deviations

19a. Adherence to protocol and how this is assessed

Adherence to protocol is defined as: 1) participant meets eligibility criteria prior to randomization; 2) all planned assessments are completed; and 3) the patient receives the complete dose of the blinded study drug intravenously over a course of 40 minutes, initiated after induction of anesthesia and completed before extubation or transfer to the post-anesthetic recovery area.

19b. How adherence to protocol will be presented

Adherence to protocol will be presented as a proportion.

19c. Protocol deviations

Emergency protocol deviations are defined as those occurring in an emergency situation where departure from the protocol (such as unblinding the study drug) is required immediately to protect the life or physical well-being of the participant.

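### SAP 27a gives the primary model random intercepts and slopes without defining time, the Day 1-3 pooling or the contrast; if the slope is linear through Day 14, the test need not hold 5%

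*SAP*

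**What the plan says.** SAP 27a calls the primary analysis an MMRM with treatment, time and their interaction as fixed effects. It pools the Day 1, 2 and 3 MADRS scores into one time point. On the within-patient structure it says: "The data will be modeled with random intercepts and random slopes to account for variation in baseline scores and postoperative trajectories".

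SAP 12 brings the later visits in: "Additional outcomes collected at postoperative Day 5, 7, and 14 will be used for statistical model building and exploratory analyses". SAP 26a defines the primary outcome as MADRS over Days 1 to 3, and 26c lists the Day 5, 7 and 14 scores as exploratory. SAP 16 sets the error rate: "We will use an uncorrected two-sided alpha of 0.05 as a cutoff for statistical significance". SAP 17 presents the pooling of the three days as the protection against type I error.

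SAP 4b explains why the endpoint was widened to three days: "To account for the likely increased variability of postoperative recovery in this broader population". The only variability figures are the planning SDs of change in SAP 11: "participants had a mean decrease of 10.9 points (SD=8.9) in MADRS total score relative to pre-infusion scores", against a "mean decrease of 2.8 points (SD=3.6) with midazolam".

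Neither the SAP nor the Protocol (section 8C, Analysis Plan, item 3) states whether time is continuous or categorical, whether Days 1-3 are averaged or kept as three rows, the residual covariance, the tested contrast, or the degrees of freedom.

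**The concern.** A random slope meant to capture postoperative trajectories would ordinarily be coded as one slope on time. It then says that each patient's departure from the group mean grows in a straight line from Day 0 to Day 14. The plan looks for an effect within the first three days, in a population it expects to recover more variably. If patients differ in how far their score moves just after surgery, a 14-day line cannot follow that. The model assigns most of the jump to independent residual noise, and the standard error of the Day 1-3 contrast comes out too small. If deviations instead decay smoothly over days, the error runs the other way.

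With complete data the point estimate is unaffected. At stake are the standard error, the 95% confidence interval and the p-value of the single primary test. SAP 27b does not vary the covariance, and its items 3 and 4 again use an MMRM. Choosing among the possible readings after unmasking would leave the p-value open to an undeclared choice.

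**Working it through.** **1. The plan's own figure.** SAP 11 says: "we computed an estimated total sample size of 38 participants at a two-sided alpha level of 0.05 and 80% power". With a difference of 10.9 - 2.8 = 8.1 and SD 8.9 in both arms, n per arm = 2 × (1.96 + 0.8416)² × 8.9² / 8.1² = 2 × 7.849 × 79.21 / 65.61 = 18.95. That rounds to 19 per arm, or 38 in total, so the figure reproduces. It rests on an SD of change only and gives no within-patient covariance with which to calibrate the mixed model. The covariance values below are therefore assumptions.

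**2. Why a line cannot absorb a jump.** Suppose the pooled window sits at Day 2. To give patient deviations an SD of 8 there, the slope SD would have to be 8 / 2 = 4 points per day, which implies an SD of 4 × 14 = 56 points at Day 14. The fit cannot accept that, so the jump goes into the residual.

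**3. One case in full.** Assume intercept SD 5, residual SD 3, a persistent jump of SD 8, 20 per arm, and Days 1-3 averaged.
- True variance of change per patient: 8² + 3² + 3²/3 = 64 + 9 + 3 = 76.
- True SE of the group difference: √(2 × 76 / 20) = 2.76.
- SE reported by the best-fitting random-intercept, linear-slope model: 1.90.
- False-positive rate: 2 × [1 - Φ(1.96 × 1.90 / 2.76)] = 2 × [1 - Φ(1.35)], about 17.7%. Simulating 600 null trials gave 17.3%.

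**4. Other assumed covariances.** Large-sample rates for change from baseline, linear slope through Day 14. The jump fades to 30% by Day 14, with intercept SD 5 and residual SD 3. The last row uses SD 6 and residual SD 2.

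| Patient deviations | Days 1-3 as three rows | Days 1-3 averaged |
|---|---|---|
| Jump SD 8 | 24.5% | 16.1% |
| Jump SD 6 | 19.8% | 12.7% |
| Jump SD 4 | 13.6% | 8.3% |
| Jump SD 2 | 7.5% | 4.2% |
| Serial correlation, 3-day range | 4.1% | 1.2% |

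Coding the window by actual day or as Day 2 makes little difference. Testing the Day 1-3 level instead of the change gives about 6-10% for jumps of SD 4 to 8.

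**5. Anchoring to the SAP's SDs of change.** Averaged window, change contrast, residual SD varied from 1.5 to 5 where that is compatible with the SD of change:
- SD of change 3.6: about 3% to 16%
- SD of change 6.8, the root mean square √((8.9² + 3.6²)/2): about 5% to 24%
- SD of change 8.9: about 9% to 26%

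**6. Specifications that hold.** With categorical time and unstructured covariance, simulated rates were 4.2% to 5.8% in six scenarios (600 trials each, simulation error about 0.9 points). ANCOVA on the Day 1-3 mean, and a t-test on change, gave 4.7% to 5.3% in a separate set of simulations. With Day 0 plus three Day 1-3 rows and two-level time, the random slope is the patient's own jump; the large-sample rate is 5.0%, and simulation gave 3.7% to 7.0% (300 trials each, error about 1.3 points).

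**7. Readings that cannot be fitted.** If Days 5-14 are dropped and Days 1-3 averaged, each patient has two values. These supply three variances and covariances for four parameters (intercept variance, slope variance, their covariance, residual). If patient effects are given to all five categorical times with an averaged window, 15 random-effect parameters plus a residual face 15 observable moments.

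The simulations assumed normal errors and complete data, and used t with 38 degrees of freedom.

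**The case against.** The strongest reply is that a linear slope is not in the text. SAP 27a speaks of slopes, names no time scale, calls the model an MMRM, and pools three days into one time point, which suits categorical time at least as well. SAP 26 lists Days 5-14 as exploratory, so SAP 12 does not settle whether they enter the primary fit. The two-level reading is available and valid. All of this stands, and it is why the point is conditional. It does not rescue the sentence: the text permits a miscalibrated model, models that cannot be identified, and a valid one that the SAP never states.

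A second reply is that the documents speak of postoperative MADRS, not change from baseline, and that testing the level roughly halves the larger inflation figures. This also stands, but 6-10% is still above 5%.

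Third, the planning SDs do not establish a jump. A reader might take √(8.9² - 3.6²) = 8.1 as the ketamine arm's jump SD. That requires the comparator's changes to contain no patient heterogeneity and both arms to share one residual variance, and SAP 11 supports neither. The figure is not relied on here.

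Finally, an unidentifiable model would show itself at fitting and not as a silently wrong p-value. That is correct; the risk to the p-value comes from the linear-slope fit.

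**Conclusion.** The point holds conditionally. SAP 27a states a covariance rule but leaves undefined what determines its behaviour. If the rule is fitted as one linear slope from Day 0 to Day 14, the Day 1-3 test need not hold its two-sided 5%. With 20 per arm, intercept SD 5, residual SD 3 and jumps of SD 4 to 8, the rate is about 8-25% for change from baseline and 6-10% for the level. With serially decaying correlation it can fall to about 1-4% for change.

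A reader might infer that these ranges are the trial's actual error rate, or its limits. The documents do not support that. Jump SD, residual SD, decay and correlation are all assumed, and other choices gave from under 1% to about 34%. With a jump of only SD 2 and averaged days, the rate was 4.2%, close to nominal.

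A reader might also blame the jump for the conservative end. That end comes from smoothly decaying correlation, or from forcing one residual variance on a three-day mean: data with a truly linear slope gave 1.3% to 2.8% with averaged rows. Nor do the documents show that the sponsor will fit the linear version. What they show is that nothing prevents it, and that no planned sensitivity analysis would reveal it.

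**What to change.** Before unmasking, replace the random-intercept and random-slope sentence in SAP 27a with the following specification:
- Time is categorical: baseline, Day 1-3, Day 5, Day 7 and Day 14.
- Each patient's Day 1-3 MADRS scores are averaged into one visit value, with a stated rule for when some of the three are missing.
- The within-patient covariance is unstructured over those five visits, with Kenward-Roger degrees of freedom.
- The primary test is a single treatment contrast at the Day 1-3 visit, written out as either the level or the change from baseline.
- If the model does not converge, the fallback is ANCOVA of the Day 1-3 mean on baseline MADRS.

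Use the same specification for the MMRMs in 27b items 3 and 4.

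The cost is SAP wording, with no new data or visits. The downside is small: an unstructured five-visit matrix may not converge with 40 patients, which the fallback covers. Kenward-Roger itself was not simulated here; the checks used 38 degrees of freedom with complete data.
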